7.3.2.2 Other events that require the investigator to notify without delay the sponsor

Adverse events deemed "medically significant" by the investigator even if they would not be classified as serious according to the definition here-above.

- Infections grades 4 (Life-threatening consequences; urgent intervention indicated) and 5 (death) according to CTCAE as well as all superinfections grade ≥3 and viral reactivation grade ≥ 3
- For COVID-19 patients, any worsening of SARS-CoV 2 infection grade ≥ 3 should be notified to the sponsor without delay.
- Bleeding in the gastrointestinal tract defined by clinical evidence of active bleeding and need for blood transfusion OR hemostatic endoscopic or surgical procedures
- Hyperglycemia grades 3 (insulin therapy initiated), 4 (Life-threatening consequences; urgent intervention indicated) and 5 (death) according to CTCAE
- Hypernatremia grades 4 (>160 mmol/L; life-threatening consequences) and 5 (death),
- Coma,
- Stroke
- Muscle weakness grades 3 (distal motor deficit), 4 (mild-to-moderate proximal motor deficit), and 5 (severe proximal motor deficit) according to MDRS scale.

The investigator must notify the sponsor without delay on the day the investigator becomes aware of these adverse events, in the same manner and within the same deadline as for serious adverse events (see above).

7.3.2.3 Serious adverse events that do not require the investigator to notify the sponsor without delay

Expected SAEs that were prespecified as trial outcomes will not be reported as SAEs and are only recorded in the case report forms.

- **Observational phase**: All AE and SAE will be collected in the case report forms and will not require notification to the sponsor. These can be analyzed at the request of the DSMB committe.
- Interventional phase: All of the SAE listed below will be collected in the case report form and will not require notification to the sponsor
 - Normal and natural course of the condition:
 - planned hospitalisation for monitoring the condition under investigation [no deterioration in the participant's condition compared to baseline],
 - hospitalisation for routine treatment or for monitoring of the condition under investigation, not associated with a deterioration in the participant's condition,
 - emergency hospitalisation at inclusion or prolongation of hospitalisation after inclusion for monitoring the condition under investigation

• Death occurred after 90 days

The primary objective of the study is to compare the effect hydrocortisone plus fludrocortisone vs. placebo on a composite of death or persistent organ dysfunction – defined as continued dependency on mechanical ventilation, new renal replacement therapy, or vasopressors – assessed at 90 days on intensive care unit (ICU) adults and having different biological profiles for immune responses and corticosteroids bioactivity

deaths after 90 days do not need to be notified to the sponsor without delay but will be recorded in the case report forms.

An e-CRF extraction of death will be realized every year on the occasion of the preparation of the annual safety report (DSUR). This extraction will be realized by the clinical research unit and transmitted to vigilance department at [contact].

If there is any discrepancy between the groups or the mortality rate is higher than expected [state the timeto-mortality or number of patients] affecting participant safety and which requires the sponsor to take urgent safety measures, the ANSM (French Health Products Safety Agency) will be informed about the emerging safety issue without delay.

- All serious adverse effects of grade 3 or less according to CTCAE and reported in the section "Effets indésirables" of the SPCs of the investigationals medicinals products
- All adverses events of grade 3 or less according to CTCAE related to biological test and blood sample.
- Special circumstances
- Hospitalisation for a pre-existing illness or condition
- Hospitalisation for a medical or surgical treatment scheduled prior to the study
- Admission for social or administrative reasons
- Adverse events potentially related to treatments prescribed as part of the care provided during the study follow-up

The investigator must report these adverse events to the relevant regional pharmacovigilance centre, Centre Régional de Pharmacovigilance (CRPV).

7.3.2.4 Period during which SAEs must be notified without delay by the investigator to the sponsor

The investigator must notify the sponsor without delay of any serious adverse events as defined in the corresponding section:

- from the date on which the participant begins treatment with an investigational medicinal product (interventional period)
- throughout the whole follow-up period required for the trial
- until 90 days after the end of the participant's treatment with the investigational medicinal product.
- indefinitely, if the SAE is likely to be due to the investigational medicinal product or to the study interventions (e.g. serious reactions that could appear long after exposure to the medication)

7.3.2.5 Procedures and deadlines for notifying the sponsor

The initial notification of an SAE must be provided in a written report signed by the investigator using a SAE notification form specific to the study and intended for this purpose (in the case report form).

Each item in this form must be completed by the investigator so that the sponsor can carry out the appropriate analysis.

The initial notification to the sponsor of a serious adverse event must be quickly followed by an additional detailed written report (or reports) so that the case outcome may be monitored by the Safety Department of the Clinical Research and Innovation Delegation (DRCI) within the APHP or to provide further information.

Whenever possible, the investigator will provide the sponsor with any documents that may be useful (medical reports, laboratory test results, results from additional examinations, etc.). These documents

must be non-identifying. In addition, the documents must include the following: study acronym, number and participant's initials.

Any adverse event will be monitored until fully resolved (stabilisation at a level considered acceptable by the investigator, or return to the previous state) even if the participant has left the study.

The initial notification, the SAE follow-up reports and all other documents must be sent to the sponsor's Safety Department by email ([contact]). It should be noted that it is possible to send SAE reports to the Safety Department by fax to [name] only in the event of a failed attempt to send the SAE report by email (in order to avoid duplication).

As this study uses an e-CRF:

- the investigator completes the SAE notification form in the e-CRF, then validates, prints, and signs the form before sending it by email;
- if it is not possible to connect to the e-CRF, the investigator should complete, sign, and send the SAE notification form to the Safety Department. As soon as the connection is restored, the SAE notification form in the e-CRF must be duly completed.

The investigator must respond to all requests from the sponsor for additional information. For all questions relating to the notification of an adverse event, the Safety Department can be contacted via email: [contact].

7.3.3 Role of the sponsor

The sponsor, represented by its Safety Department, shall continuously, throughout the trial, assess the safety of each investigational medicinal product.

The sponsor assesses:

- the **seriousness** of all the adverse events reported
- the **causal relationship** between these events and each investigational medicinal product, All serious adverse events which the investigator and/or the sponsor reasonably believe may have a causal relationship with the investigational medicinal product are classified as suspected serious adverse reactions.
- the **expected or unexpected nature** of the serious adverse reactions Any serious adverse reaction whose nature, severity, frequency or outcome is inconsistent with the safety information described in the summary of product characteristics is considered unexpected.

The sponsor, represented by its Safety Department, assesses the expected/unexpected nature of a serious adverse reaction based on the information described below.

- For serious adverse events likely to be related to the investigational medicinal products: refer to the SmPC for HYDROCORTISONE UPJOHN 100 mg" laboratory origin : Serb and to the SmPC for "FLUCORTAC 50 μg" laboratory origin : H.A.C. Pharma.
- To the extent that the information contained in the marketing authorizations is likely to change, it is necessary to ensure at the time of the prescription of the drugs compliance including contraindications, warnings and precautions of use, drug interactions. Refer to the information available on the Public Drug Database, accessible via the Internet at the following address : http://base-donnees-publiqu.me edicament.sgouv.fr/.

The sponsor will report all suspected unexpected serious adverse reactions (SUSARs), within the regulatory time frame, to the ANSM:

- The sponsor must send the initial report without delay upon learning of the unexpected serious adverse reaction if is fatal or life-threatening, or otherwise within 15 days from learning of any other type of unexpected serious adverse reaction;
- All additional, relevant information must be declared by the sponsor in the form of follow-up reports within a period of 8 calendar days starting from when the sponsor had this information.

Any suspected unexpected serious adverse reaction must also be declared electronically using the Eudravigilance European adverse drug reactions database managed by the European Medicines Agency (EMA).

The sponsor must notify all the investigators involved about any information that could adversely affect the safety of the research participants.

7.3.3.1 Blindness

After unblinding by the sponsor and if the patient is receiving the product under investigation: the case will be reported without delay as a suspected unexpected serious adverse reaction. If the patient is receiving the comparator product: the sponsor will reassess the unexpected nature of the adverse reaction based on the reference document for the comparator product identified in the protocol.

In exceptional situations, if the study involves a condition with a high mortality and/or morbidity rate, and if the ANSM grants permission at the request of the sponsor as part of the clinical trial authorisation application, the methods for unblinding and for reporting suspected unexpected serious adverse reactions can be modified. These methods will then be defined thoroughly in the study protocol.

7.3.3.2 Analysis and declaration of other safety data

This means any new information that prompts a reassessment of the risk/benefit ratio of the trial or of the product under investigation, or which could be sufficient to consider changes to the use of the product, the trial procedures or trial documentation, or the suspension, cancellation or amendment of the research trial or of other similar trials.

The sponsor will inform the competent authority and the Research Ethics Committee without delay upon knowledge of any emerging safety issue and, if applicable, describe what measures have been taken.

Following the initial declaration of any emerging safety issue, the sponsor will address to competent authorities any additional relevant information about the emerging safety issue in the form of a follow-up report, which must be sent no later than 8 days after learning of the information.

7.3.3.3 Annual safety report

Once a year for the duration of the clinical study, the sponsor must produce an annual safety report (Development Safety Update Report - DSUR) which includes, in particular:

- a safety analysis for the research participants,
- a description of the patients included in the study (demographic profile etc.)
- a list of all the suspected serious adverse reactions that occurred during the period covered by the report,
- summary tables of all the serious adverse events that have occurred since the start of the study,

The report must be delivered no later than 60 days after the anniversary of the date on which the ANSM authorised the trial.

7.3.4 Data Safety Monitoring Board (DSMB)

A DSMB will be established for this trial. The DSMB must hold its first meeting before the first participant is enrolled and ideally before the protocol is submitted to the competent authority and the CPP (Research Ethics Committee).

All missions as well as the specific operating procedures of the DSMB are described in the study's DSMB charter.

The DSMB members are:

- Pr. [name], service des Maladies Infectieuses et Tropicales, hôpital Pitié Salpétrière.
- Pr [name], service des Maladies Infectieuses et Tropicales, hôpital Saint-Louis – APHP.
- Pr [name], pharmacologue, Haute Autorité de Santé (fin de fonction fin juin 2020).
- Pr [name], réanimateur, Chef de service de médecine intensive adutte au Centre Hospitalier Universitaire Vaudois (CHUV), Suisse

The DSMB will operate in accordance with the sponsor's procedures. The DSMB works in an advisory capacity only and the sponsor retains all decision-making authority.

7.3.5 Discontinuation of the Study

In the event of a premature discontinuation of the clinical trial (e.g. sponsor decision to discontinue the trial due to safety concerns, alternative therapy newly available that may benefit research subjects), a notification will be sent to ANSM and the CPP no later than 15 days after the date of the discontinuation. A discontinuation procedure will be made available when necessary (Figure 5).

7.3.6 Dissemination Policy

Dissemination will be done via an integrated knowledge translation strategy.

Plans for end-of-study dissemination include presentations at major international conferences, publications in high-impact journals and, building on experience with social media developed during previous trials, dissemination of our results via social media platforms and discussion forums managed by partner organizations.

8.2 STEERING COMMITTEE

The Steering Committee consists of intensivists, statisticians, research methodologists, and stakeholders (including patient representatives) and will meet by quarterly teleconference. The Steering Committee will provide guidance and direction to the overall trial.

8.3 DATA SAFETY MONITORING BOARD COMMITTEE

There is need to establish a DSMB committee for this trial as the drugs used in this trial are corticosteroids, , which is also on line with the trial categorisation as Risk B via the APHP logistic score.

9 STATISTICAL ANALYSIS

9.1 SAMPLE SIZE DETERMINATION

We will enroll a total of at most 1800 patients. Sites are expected to enroll at least 1 or 2 patients per month.

Adaptive outcomes

The goal is to develop an adaptive clinical trial design which evaluates the therapeutic intervention of targeted therapy, identifies subset of subjects who respond better to the experimental therapy.

Sequential analyses will use the number of vasopressor-free days at day 28 as the measure of efficacy, and the occurrence of severe adverse events within the first 28 days as the measure of toxicity. According to the literature (the APPROCCHS trial), the number of vasopressor-free days at day 28 in the hydrocortisone+fludrocortisone group was 17.1 ± 10.8 versus 15.0 ± 11.1 in the placebo group. Thus, a sample of 176x2=352 patients achieves 80.04 % power to reject the null hypothesis of equal means when the mean difference between arms is 3 days with SD of 10 days, and with a significant level (alpha) of 0.05 using a two-sample t-test. For interactions to be detected with the same power as the overall effect, sample sizes should be inflated (Brookes 2004); estimated here at a multiple of fourfold; therefore, to handle potential dropouts, a sample of 1800 patients was considered to be enrolled.

Note that Bayesian inference will be used for sequential analyses, so that no inflation of type I error rate is to be corrected.

Primary outcome

To detect a 10% absolute risk reduction (from 45% to 35%) in the day 90 mortality, a sample size of 373 evaluable patients per arm (thus a total of 746 patients) is required to reach a 80% power. The planned sample of 1800 patients will achieve a 99.16%

power to reject the null hypothesis of equal mortality when the difference between arms is 10% overall, and with a 5% alpha level.

Sample sizes were computed using PASS 15 software (2017).

The power to detect this difference within each group of analysis will depend on the prevalence of each biomarker of interest.

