4.1.2 Interventional phase

4.1.2.1 ELIGIBILITY CRITERIA (INTERVENTIONAL PHASE)

4.1.2.1 Inclusion Criteria (interventional phase)

- 1) Patients \geq 18 years old;
- 2) Admitted to the ICU with proven or suspected infection as the main diagnosis;
 - 3) Community acquired pneumonia related sepsis OR vasopressors dependency (norepinephrine, epinephrine, vasopressin, dopamine, phenylephrine) OR septic shock (Singer 2016: vasopressor to maintain mean blood pressure of at least 65 mmHg and lactate levels above 2 mmol/l) OR acute respiratory distress syndrome (ARDS Ranieri 2012: a- acute onset, i.e. within one week of an apparent clinical insult and with progression of respiratory syndrome, b-bilateral opacities on chest imaging not explained by other pulmonary pathologies, e.g. pleural effusion, atelectasis, nodules etc, c- no evidence for heart failure or volume overload, d-PaO2/FiO2 ≤ 300 mm Hg, PEEP ≥ 5 cm H2O

4) Patient who has signed an informed and written consent whevener he/she is able of consent, if not, if not ascent from his/her representant whenever he/she is present at time of screening for inclusion

- 5) Patients who have been tested for one or more RECORDS specific biomarkers
 - o CIRCI
 - o Endocan
 - o GILZ <
 - o CPD
 - o Transcriptomic SRS2
 - o Endotype B
 - o PCR COVD-19
 - o PCR Influenza
 - o PCR other respiratory virus

6) Affiliation to a social security system or to an universal health coverage (Couverture Maladie Universelle, CMU);

7) Patients under guardianship or curatorship will be included;

8) Patients in case of simple emergency (legal definition) will be included.

RECORDS" protocol, version 4.0 of 03/03/2021

16/61

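### Section 9.1 sizes the trial for interactions on an effect larger than the data it cites, and with a fourfold factor that is right only for a 50:50 marker and an interaction as large as the overall effect

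*Protocol*

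**What the plan says.** Under Adaptive outcomes in protocol section 9.1, the sequential analyses use vasopressor-free days at day 28 as the efficacy measure. The protocol reports that in a previous trial of the same drugs the result with active treatment "was 17.1 ± 10.8 versus 15.0 ± 11.1 in the placebo group". The next sentence opens with the word Thus and states that "a sample of 176x2=352 patients achieves 80.04 % power to reject the null hypothesis of equal means", and that this holds "when the mean difference between arms is 3 days with SD of 10 days", "with a significant level (alpha) of 0.05 using a two-sample t-test".

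The section then says that sample sizes must be inflated if interactions are to be detected with the same power as the overall effect. The inflation is "estimated here at a multiple of fourfold". With an allowance for dropout, whose rate is not given, the total becomes 1800.

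No planning prevalence is given for any biomarker. The Primary outcome paragraph of the same section does say: "The power to detect this difference within each group of analysis will depend on the prevalence of each biomarker of interest". That sentence refers to the 10% absolute difference in the primary outcome, not to the fourfold factor.

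**The concern.** Two steps in the argument for 1800 do not follow from what the section itself states.

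First, the effect is raised from 2.1 to 3 days and the SD lowered from about 11 to 10. Both changes favour a smaller sample. No reason is given, and the wording presents the new values as a consequence of the cited trial.

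Second, a factor of four is the inflation for an interaction test only when the marker splits the patients in half and the interaction is as large as the overall effect. Neither condition is stated.

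Section 9.2.1 makes detection of treatment-by-biomarker interactions the aim of the sequential analyses. A reader who takes the 80% at face value would overestimate what a finding of no interaction shows, above all for uncommon markers.

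**Working it through.** **Inputs from section 9.1.** Alpha 0.05; 176 per arm; planned difference 3 days, SD 10; cited results 17.1 (SD 10.8) and 15.0 (SD 11.1); factor 4; total 1800. Allocation is 1:1 (study summary). Sidedness is not stated; two-sided is inferred because it reproduces the stated power, whereas one-sided would give about 88%. **Assumed:** marker prevalence p from 10% to 50%.

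**1. The plan's own figure.** Standardised effect 3/10 = 0.300. A two-sample t-test with 176 per arm has 80.1% power (noncentral t), which agrees with the stated 80.04%. Then 352 × 4 = 1,408. Going from 1,408 to 1800 implies a loss of 1 − 1408/1800 = 21.8%.

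**2. The cited data.** Difference 17.1 − 15.0 = 2.1. Pooled SD √[(10.8² + 11.1²)/2] = 10.95. Standardised effect 2.1/10.95 = 0.192. The planned effect is 0.300/0.192, or about 1.6 times as large. At the 352-patient step, which is intermediate and not the trial size, power falls from 80.1% to 43.4%. Changing only the difference gives 50.2%; changing only the SD gives 72.7%. For 80% power, 428 per arm (856 in total) are needed, and 856 × 4 = 3,424.

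**3. The inflation factor.** With N patients randomised 1:1, the variance of the overall difference is 4·SD²/N. The variance of the difference between the effects in marker-positive and marker-negative patients is

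4·SD²/(Np) + 4·SD²/[N(1−p)] = 4·SD²/[N·p(1−p)].

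For an interaction as large as the overall effect, the inflation is therefore 1/[p(1−p)]: 4.0 at p = 50%, 4.76 at 30%, 6.25 at 20% and 11.1 at 10%.

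**4. Interaction power.** With the normal approximation, power = Φ(δ/SE − 1.96), where SE = 2·SD/√[N·p(1−p)]. Two examples:

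- N = 1,408, p = 50%, δ = 3, SD = 10: SE = 20/√352 = 1.066; 3/1.066 − 1.96 = 0.85; power 80%.
- N = 1800, p = 50%, δ = 2.1, SD = 10.95: SE = 21.90/√450 = 1.032; 2.1/1.032 − 1.96 = 0.07; power 53%.

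| Difference / SD | Evaluable | p = 50% | 30% | 20% | 10% |
|---|---|---|---|---|---|
| 3 / 10 | 1,408 | 80% | 73% | 62% | 39% |
| 3 / 10 | 1,800 | 89% | 83% | 72% | 48% |
| 2.1 / 10.95 | 1,408 | 44% | 38% | 30% | 19% |
| 2.1 / 10.95 | 1,800 | 53% | 46% | 37% | 23% |

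At 3/10 with all 1800 evaluable, power is at least 80% when p(1−p) is at least about 0.194, that is, for p down to about 26%.

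**5. The overall effect.** At 2.1/10.95 with 900 per arm: SE = 10.95 × √(2/900) = 0.516; 2.1/0.516 − 1.96 = 2.11; power 98%.

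**The case against.** The strongest reply is that nothing has been miscalculated. The 80.04% is explicitly conditional on 3 days and SD 10, and it reproduces. A target above the cited average may be deliberate, since the trial looks for subsets that respond better. This stands: the fault lies in unsupported planning inputs, not in arithmetic. It does not rescue the wording, which derives the target from the cited result instead of declaring it a choice.

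It is also fair that the fourfold factor alone does limited damage. On the plan's own effect, with all 1800 evaluable, 80% holds down to about 26% prevalence. Section 3 expects little loss to follow-up, though it says so of day 90 outcomes. Section 1.3 suggests that almost half of patients have poor adrenal activity, which would suit the factor for the CIRCI marker. No comparable hint is given for the others.

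Four stronger readings are tempting and are not supported:

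- **The trial as a whole is underpowered.** Overall power is 98% at the cited figures, and the 43% for 352 patients describes an intermediate step.
- **Few patients will have each marker measured.** The entry rule is "Patients who have been tested for one or more RECORDS specific biomarkers", but that is a minimum. Sections 5.3 and 5.15 schedule a Synacthen test, respiratory virus PCR and blood for further biomarkers at baseline.
- **Effective cohorts will be dropped.** Section 9.2.1 decides by posterior probabilities with thresholds, not by a 5% interaction test. The powers above are not the operating characteristics of that rule.
- **The 99.16% for the primary outcome is mislabelled.** Section 9.1 already says that it is for an overall difference, and adds the prevalence caveat.

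**Conclusion.** The justification of 1800 is wrong as written. Its stated inputs do not follow from the data cited one sentence before, and its claim of equal power for interactions holds, at 1,408 evaluable patients, only near a 50:50 marker. At the cited 2.1 days and SD 10.95, interaction power is at most 53%, even with an ideal split and no dropout.

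This rests on a two-sided 5% test, an interaction as large as the overall effect, and the cited trial as a relevant basis for planning. The prevalences other than 50% are assumptions. A larger interaction would need fewer patients; a smaller one, more. The point concerns what the protocol claims for its sample size. It gives no reason to doubt the overall comparison, and it is a correction to make rather than an obstacle to the trial.

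**What to change.** Keep the cap of 1800 and restate section 9.1 as follows.

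1. Replace Thus by a statement that 3 days with SD 10 is a target larger than the cited result of 2.1 days with SD about 11, and give the reason for choosing it.
2. Beside it, give the power of 1800 patients at 2.1 days and SD 10.95: 98% for the overall effect, and at most 53% for an interaction of that size. Do not quote 43% for 352 patients as though it described the trial.
3. Replace fourfold by 1/[p(1−p)], and say that it assumes an interaction as large as the overall effect.
4. Tabulate interaction power by prevalence (for example 50, 30, 20 and 10%) on one evaluable number throughout, either 1,408 or 1,800, and state the dropout rate that this number implies.

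The cost is a paragraph and a small table. No patients are added and no decision rule changes; the stated interaction power becomes less favourable.
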